2 = Definitely abnormal size or morphology, possible metastasis (intermediate suspicion)

3 = Markedly abnormal size and morphology, likely metastasis (high suspicion)

DWI Images

0 = Normal diffusion

1 = Low level of diffusion restriction when compared to adjacent normal appearing lymph nodes (low suspicion)

2 = Slightly higher level of diffusion restriction when compared to adjacent normal appearing lymph nodes (intermediate suspicion)

3 = Definitely higher level of diffusion restriction when compared to adjacent normal appearing lymph nodes (high suspicion)

Note: In cases of nonhomogenous intensity on DWI and ADC images, the grade will be determined on the basis of the most suspicious area.

PET Data Analysis: The PET images will be qualitatively and quantitatively assessed. The scoring will be based primarily on the PET data, but the reader will have access to the MRI data for anatomic correlation and characterization of lymph node morphology. For PET data analysis, a lymph node positive based on MRI criteria but negative based on fluciclovine-PET criteria will be scored as negative.

Qualitative analysis: A visual evaluation of the pelvic lymph nodes with suspected metastatic disease will be performed. As per manufacturer guidelines, lymph nodes measuring less than 1 cm in short-axis dimension will be compared to blood pool tracer activity. For lymph nodes measuring greater than 1 cm, comparison of activity will be made to the activity in the bone marrow of the L3 vertebral body. The number of positive metastatic lymph nodes and their nodal stations will be recorded.

0 = No uptake or uptake lower than appropriate reference (blood pool vs. L3 marrow)

1 = Uptake equal to reference (low suspicion)

2 = Uptake slightly greater than reference (intermediate suspicion)

3 = Uptake definitely greater than reference (high suspicion)

Quantitative analysis: Nodes scored as intermediate or high suspicion based on MRI and/or PET will undergo further quantitative analysis.

Standardized uptake values (SUVs): The maximum SUV will be measured. Additionally, the mean SUV and metabolic tumor volume will be measured based on a 40% isocontour.

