Lesion to blood pool and marrow ratios: Tissue SUV is a simple uptake ratio of activity in an area of interest compared to a normalized tissue background level. As stated in section B, activity in lymph nodes measuring less than 1 cm in short-axis dimension will be compared with activity in the blood pool and a lesion:blood pool activity ratio will be calculated. For lymph nodes measuring greater than 1 cm in short-axis dimension, activity will be compared to activity in the L3 vertebral body marrow and a lesion:marrow activity ratio will be calculated..

Dynamic PET analysis: Time-activity curves (TACs) will be generated for pelvic lymph nodes scored as intermediate or high suspicion on visual analysis. Additionally, TACs will be generated for three reference pelvic lymph nodes scored as normal. The maximum SUV at peak fluciclovine uptake, the time to peak, and the shape of the TACs over the 8 min dynamic acquisition (rising, plateau, washout) will be recorded. This analysis is exploratory as the role of dynamic fluciclovine-PET for the initial staging of prostate cancer is not established.

KEY ANALYSIS FOR SPECIFIC AIM 1

Based on the consensus PET and MRI scoring, the total percentage of nodal scoring discrepancies will be calculated. Although the total number of patients is small, a total of 165 pelvic nodal stations will be examined. In this pilot study, a discrepancy between MR-only and fluciclovine-PET/MR greater than 10% would motivate a larger study with more rigorous references standards including histopathology.

KEY ANALYSIS FOR SPECIFIC AIM 2

This study will use the nomograms routinely used by the UAB urology service in assessing newly diagnosed prostate cancer. The use of nomograms is necessary, as we will not routinely obtain histopathological verification in these high-risk, nonoperative patients in this study. Expected frequencies of lymph node metastases based on patient risk factors will be compared to observed frequencies of lymph node metastases in specific aim 1 on mpMRI alone, fluciclovine-PET/MRI, and assuming that discrepant nodes between imaging modalities (i.e. positive on one, negative on other) will be counted as positive, a combination of the two modalities that includes discrepant nodes. The assessment that most closely matches the expected frequency based on the nomogram will be considered most accurate, although small sample size will require larger studies for confirmation.

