5.0 Study Parameters

5.1 Primary Endpoints

- [¹⁸F]fluciclovine PET/MRI results for primary lesion and regional nodal metastases
- Concordance between [¹⁸F]fluciclovine PET/MRI results and multiparametric prostate MRI results
- Detection of organ-confined disease, regional nodal metastases, extracapsular extension, and seminal vesicle invasion [¹⁸F]fluciclovine PET/MRI in expected frequencies based on risk-predictor models and nomograms

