6.2 Sample Size Determination

This is a pilot study that may warrant a larger study with increased power to determine statistical significance if expected results are observed. We plan to enroll 15 patients, primarily determined by budgetary constraints and feasibility of patient recruitment in one year. No formal power calculations were used in the generation of the sample size. The primary end point of the study is to estimate percentage of high-risk prostate cancer patients whose metastasis can be detectable early by using of [¹⁸F]fluciclovine-PET/MRI comparing using standard care of mpMRI imaging. According to risk-prediction models and nomograms used in routine clinical practice, approximately 20-30% of patients with high-risk prostate adenocarcinoma will be diagnosed with nodal metastases. We expect that using [¹⁸F]fluciclovine PET/MRI will achieve similar results, e.g. 30% for early detection of metastasis without invasive procedures, and using mpMRI will result in less of detection of metastasis, e.g. 20%-25%. A size of 15 will provide a two-sided 95% confidence intervals (CI) for point estimate (% of metastasis) from 9.7% to 58.4% when the true estimate is 30% using Clopper-Pearson method. Table below shows the 95% CI when the true estimate varies.

Proportion (%) (estimate of metastasis)	Sample size	95% CI Lower limit	95% CI Upper limit
20	15	4.3	48.1
25	15	6.9	53.4
30	15	9.7	58.4

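### Aim 2 calls the read whose total is closest to the nomogram the most accurate; totals hardly tell added true positives from added false ones, and more patients do not help

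*Combined protocol and SAP*

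**What the plan says.** Section 4.6.3, in its key analysis for Specific Aim 2, sets out the comparison: "Expected frequencies of lymph node metastases based on patient risk factors will be compared to observed frequencies of lymph node metastases". Three reads are compared: mpMRI alone, PET/MRI, and a combination that counts every discrepant node as positive. The rule follows: "The assessment that most closely matches the expected frequency based on the nomogram will be considered most accurate". The sentence ends with its only qualification, "although small sample size will require larger studies for confirmation". No tie rule is given, and the text does not say whether frequency is counted per man or per nodal station.

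Section 5.1 lists among the primary endpoints the detection of disease "in expected frequencies based on risk-predictor models and nomograms", whereas section 6.1 makes this the secondary objective. Section 6.2 gives the rates per patient. For the nomograms it says that "approximately 20-30% of patients with high-risk prostate adenocarcinoma will be diagnosed with nodal metastases"; it expects about 30% on PET/MRI and 20-25% on mpMRI.

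Other sections describe further evidence. Section 1.1 calls the risk models an indirect assessment of accuracy. Sections 2.0 and 5.2 use the follow-up scan to help confirm baseline lesions. Section 6.4.2 estimates sensitivity, specificity and accuracy of PET/MRI with PSA level as the expected result. None of these enters the rule in section 4.6.3.

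**The concern.** Accuracy depends on whether the men called positive are the men with disease. A total cannot show this, because a missed metastasis and a false positive cancel. A read can match the nomogram total by finding the diseased men, or by missing some and wrongly calling an equal number of others. The rule gives both the same credit.

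The sample-size caveat suggests that repeating the comparison in more men would settle the matter. It would only make the rule more certain of its choice, right or wrong.

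This is the only sentence in the plan that names a most accurate read, and it concerns a listed primary endpoint. The pilot could report PET/MRI as the most accurate when it had added only false positives, or report mpMRI as the most accurate when PET/MRI was better.

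**Working it through.** **The plan's own figures.** Clopper-Pearson limits with x = p × 15 are the 2.5% quantile of Beta(x, n−x+1) and the 97.5% quantile of Beta(x+1, n−x). They give 4.33-48.09% at 20%, 6.86-53.40% at 25% and 9.74-58.42% at 30%, which agrees with the table in section 6.2. The plan attaches no figure to the Aim 2 rule.

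**Inputs.** From section 6.2: n = 15, nomogram 20-30%, PET/MRI 30%, mpMRI 20-25%, all per patient. Assumed: the unit is the man; sensitivities, overlap of the reads and the spread of individual risk are as stated in each step.

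**Rule as a formula.** With M and P the numbers of men positive on mpMRI and PET/MRI, and E the expected number, PET/MRI is preferred when |P − E| < |M − E|. If E = n × a fixed rate, disease status appears nowhere in this expression.

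**1. Nested reads, fixed rate 30% = true prevalence.** mpMRI is positive in 20%, all true. PET/MRI is positive in the same men plus 10%. The counts are trinomial (0.20, 0.10, 0.70).

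| n | PET/MRI closer | tied | mpMRI closer |
|---|---|---|---|
| 15 | 48.3% | 30.9% | 20.8% |
| 60 | 81.0% | 4.0% | 15.0% |
| 150 | 92.7% | 1.3% | 6.1% |

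mpMRI is correct in 1 − 0.10 = 90% of men. PET/MRI is correct in 100% if the extra men are true positives and in 1 − 0.10 − 0.10 = 80% if they are false positives. The table is the same in both cases. In the second, the rule prefers the worse read more often as n grows.

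**2. Non-nested reads, same fixed rate.** The PET scoring allows disagreement in both directions: "a lymph node positive based on MRI criteria but negative based on fluciclovine-PET criteria will be scored as negative". Take 15% positive on both, 5% on mpMRI only, 15% on PET/MRI only and 65% on neither, so PET/MRI is 30% and the combination 35%.

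- PET/MRI perfect: mpMRI sensitivity 15/30 = 0.50, specificity 65/70 = 0.93.
- PET/MRI worse: PET/MRI 15/30 = 0.50 and 55/70 = 0.79; mpMRI 20/30 = 0.67 and 1.00.

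The cell probabilities are the same, so the results are too. PET/MRI closer / tied / mpMRI closer is 47/28/25% at n=15 and 79/6/15% at n=60. With all three reads, sole best PET/MRI / mpMRI / combination / tie is 8/18/12/62% at n=15 and 44/13/30/13% at n=60.

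**3. E = sum of individual risks.** The reference to patient risk factors suggests this reading. With risks drawn from Beta(0.9, 2.1), mean 30%, simulation gives the chance that PET/MRI is closer:

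| Case | n=15 | n=60 | n=150 |
|---|---|---|---|
| Step 1, true v false extras | 56% v 53% | 86% v 84% | 95.5% v 94.0% |
| Step 2, perfect v worse | 57% v 50% | 84% v 80% | not run |

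The totals now carry some information. Set directly against a read unrelated to disease with 30% positive, a perfect read is closer in 50% of trials and the unrelated read in 34% at n=15. At n=300 the figures are 56% and 40%. The gap stays near 16 points.

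**4. Dependence on the nomogram rate (fixed rate, nested, n=15).** PET/MRI closer v mpMRI closer:

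| Nomogram rate | mpMRI 20% | mpMRI 25% |
|---|---|---|
| 30% | 48% v 21% | 26% v 19% |
| 25% | 40% v 39% | 23% v 31% |
| 20% | 21% v 52% | 11% v 40% |

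The preferred read changes within the plan's own 20-30% range.

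**5. Error against PET/MRI.** Let prevalence and nomogram both be 20%, mpMRI sensitivity 0.50, PET/MRI sensitivity 1.00 and both specificities 0.875. Positives are 0.20×0.50 + 0.80×0.125 = 20% and 0.20×1.00 + 0.80×0.125 = 30%. mpMRI, the worse read, is closer 52% v 21% at n=15 and 81% v 15% at n=60. With summed risks from Beta(0.6, 2.4) it is 54% v 25% and 84% v 16%.

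**The case against.** The plan is open about its reference standard. The same paragraph of section 4.6.3 says that nomograms are needed because histology will not be routine. Section 2.0 calls them, together with the follow-up scan, a surrogate for accuracy. Larger studies need not repeat this rule: a discrepancy above 10% in Aim 1 "would motivate a larger study with more rigorous references standards including histopathology", and section 2.0 foresees histopathology under Aim 2 as well. On this reading the accuracy label is a declared surrogate in an exploratory pilot.

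Much of this is fair as context, but it does not repair the rule. Explaining why a nomogram is used does not limit what a match with it can show. The follow-up scan and the PSA analysis do not enter the ranking. A later histology study would help through its reference standard, not through its size, and the sentence mentions only size.

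Three points about the numbers stand. First, the separation is not always 2 or 3 points: with individual risks it reaches 7 points in step 2, and a perfect read leads an unrelated one by about 16. Second, the sole-best figures at n=15 understate PET/MRI because ties are so common; it is best or joint best in 65% of trials, against 45% for mpMRI. Third, the per-patient unit is a choice that section 4.6.3 leaves open.

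**Conclusion.** The concern holds: the rule is wrong as written. With a fixed nomogram rate, reads with the same joint pattern of positives receive the label equally often whatever their accuracy. With individual risks the difference is 3 to 7 points at n=15 and 2 to 4 points at n=60 in the cases compared. A larger sample does not correct this: when the extra positives are false, the fixed-rate rule prefers the 80%-accurate read to the 90%-accurate one in 93% of trials at n=150. The label can go wrong in either direction within the plan's 20-30% range.

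The positive rates come from section 6.2. The sensitivities, the overlap and the risk spread are assumptions; the fixed-rate equality needs only equal cell probabilities. The consequence is limited. The only numeric trigger in the plan is Aim 1's 10% discrepancy, so what is at stake is one unsupported conclusion in a descriptive pilot of 15 men. The sentence should be changed.

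**What to change.** In section 4.6.3, delete the clause that names the closest read the most accurate, and replace it with:

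> For each read, the number of men with at least one positive node will be shown beside the sum of the men's nomogram probabilities, with the exact Poisson-binomial 95% range of counts expected if the nomogram is right. This describes calibration with the nomogram. It does not rank the reads on accuracy, which awaits a study with histopathology.

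For 15 men the range is 1-8 for a sum of 4.5 (all at 30%, or five each at 10%, 30% and 50%), 1-7 for 3.75 (all at 25%) and 0-6 for 3.0 (all at 20%). Counts of 3, 4 or 5 (20-33% positive) lie inside all of them, so the pilot could not separate the expected rates even as calibration.

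The cost is one sentence of wording and a short calculation from nomogram inputs already planned. No new data are needed. The PSA-based estimates in section 6.4.2 and the follow-up check in section 2.0 can stay, since neither ranks the three reads. The pilot gives up only a statement that its design cannot support.

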4.6.4 Safety Monitoring

Vital signs will be assessed immediately before and after injection of [¹⁸F]fluciclovine (HR and supine BP). Patients will be monitored for adverse events during injection and after completion of the imaging study. Additionally, patient's vitals (HR and supine BP) will be checked at the completion of the imaging study prior to leaving the imaging center.

4.6.5 Patient Follow-Up

Patients will be instructed to contact the UAB Department of Radiology Advanced Imaging Facility if there are any concerns about delayed side effects related to the study radiotracer. Patients will be seen in the clinic if there are any concerning study related adverse events requiring further evaluation.

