6.5.5 Adverse Event Reporting

As with many IV administered agents, [¹⁸F]fluciclovine could cause an allergic reaction that could potentially pose a threat to life (anaphylaxis). This has not been observed in limited human exposure to date. Reasonable precautions should be taken, consistent with normal radiologic and clinical facility practice. The patient should be monitored until the PET procedure is completed, and trained personnel and emergency equipment should be available per facility standards.

Qualifying Adverse Events (AEs), including Serious Adverse Events (SAEs), as defined herein, will be reported via the FDA Adverse Event Expedited Reporting System (AERS). For the [¹⁸F]fluciclovine IND we will report adverse events based on the FDA final rule for IND safety reporting requirements under 21 CFR part 312 published on September 29, 2010 and implemented on March 28, 2011. This investigational study is not a BA or BE study so 21 CFR part 320 is not applicable. Adverse events will also be reported to the UAB IRB according to their requirements.

Reporting of Serious Adverse Events (SAEs) to Blue Earth Diagnostics (BED): In addition to reporting of SAEs to the responsible IRB and Health Authority, the Principal Investigator or designee will document all SAEs that occur following receipt of [¹⁸F]fluciclovine (whether or not related to study drug) to BED. Such SAEs must be reported within 24 hours of Principal Investigator or designee becoming aware of the event. All SAE information must be recorded and faxed or scanned and emailed to:

Blue Earth Diagnostics SAE E mail:	[contact]
Tel:	[name] ([name])
[contact]

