6.5.5.1 General Definitions (from 21 CFR 312.32 (a))

Adverse Event (AE): An Adverse Event is an untoward medical occurrence associated with the use of the drug in humans, whether or not considered drug related. For this study, the drug is [¹⁸F]fluciclovine and adverse events would include any events experienced by a study participant during the Adverse Event reporting period defined in Table 1 whether or not it was considered to be related to the [¹⁸F]fluciclovine. At the conclusion of the imaging study, the imaging technologist will observe the patient and also inquire if they are back to their usual state of health. If a negative answer is received, then the physician will be called to investigate this report as a possible adverse reaction.

Adverse Reaction: An Adverse Reaction is any adverse event caused by a drug. In this study, the drug is [¹⁸F]fluciclovine.

Suspected adverse reaction means any adverse event for which there is a reasonable possibility that the IND drug caused the adverse event. For the purposes of IND safety reporting, “reasonable possibility” means there is evidence to suggest a causal relationship between the drug and the adverse event. A suspected adverse reaction implies a lesser degree of certainty about causality than adverse reaction, which means any adverse event caused by a drug.

An adverse event or suspected adverse reaction is considered “unexpected” if it is not listed in the investigator brochure or is not listed at the specificity or severity that has been observed; or, if an investigator brochure is not required or available, is not consistent with the risk information described in the general investigational plan or elsewhere in the current application.

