6.5.5.2 AE Reporting Requirements

The investigators on this protocol will report any suspected adverse events that occur after [¹⁸F]fluciclovine administration and within the specified follow-up period to [name] and they will work together to determine whether there was an adverse event or adverse reaction and the severity of the adverse event or reaction.

All AEs will be followed by the investigators until resolution, stabilization, scientifically and clinically satisfactory explanation as to attribution and etiology is achieved, or until subject is lost to follow up.

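### After the patient leaves the imaging center, the only written adverse-event route is his own call about tracer side effects, which may miss the all-cause events that section 6.5.5 requires over a reporting period that is never stated

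*Combined protocol and SAP*

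**What the plan says.** **What must be collected.** Section 6.5.5.1 counts as an adverse event anything the participant experiences "during the Adverse Event reporting period defined in Table 1 whether or not it was considered to be related" to the tracer. Section 6.5.5.5 adds that an event judged unlikely to be related, or unrelated, stays reportable. Section 6.5.5 requires all SAEs after the tracer to go to the manufacturer ("whether or not related to study drug"), within 24 hours of the investigator or designee learning of them.

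**How it is collected on the day.** Section 4.6.4 says "Patients will be monitored for adverse events during injection and after completion of the imaging study", and that vital signs "will be checked at the completion of the imaging study prior to leaving the imaging center". Section 6.5.5 has the patient monitored until the PET procedure is over. Section 6.5.5.1 adds one active question: when imaging ends, "the imaging technologist will observe the patient and also inquire if they are back to their usual state of health".

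**How it is collected afterwards.** Section 4.6.5 tells the patient to contact the imaging facility "if there are any concerns about delayed side effects related to the study radiotracer". It also says "Patients will be seen in the clinic if there are any concerning study related adverse events requiring further evaluation". No telephone call, visit or question about the interval is described.

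**Over what period.** Section 6.5.5.1 points to Table 1. Section 6.5.5.2 covers events after administration and "within the specified follow-up period". Section 6.5.5.5 refers to a period set by the protocol, or by applicable guidance, regulation or policy.

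**The concern.** The definition is all-cause, but the route after departure is filtered by cause, and the patient does the filtering. A man who has an event and does not connect it with the injection has no instruction to mention it. If the event is an SAE, the manufacturer should still receive it, but the 24-hour clock starts only on awareness, so an event that reaches nobody starts no clock.

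The missing period adds to this. Without a stated end, nobody can say whether an event some weeks after an injection should be on the list, or whether the list is complete.

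At stake are the sponsor's ability to meet its own safety text and the in-house part of the adverse-event list that section 6.5.5.3 promises to keep up to date. The tracer is used here outside the recurrent-disease indication for which section 4.4 says it is approved, so that record has some value even in a pilot.

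**Working it through.** The documents give no figure for under-ascertainment, so there is none to reproduce. The check is mainly a comparison of sections, followed by a calculation for scale.

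**1. Requirement against procedure**

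| | Required (6.5.5, 6.5.5.1, 6.5.5.5) | Written procedure after departure (4.6.5) |
|---|---|---|
| Cause | Any | Tracer side effects as the patient sees them; clinic review for study-related events |
| Who starts it | Not stated | The patient |
| Period | Said to be defined elsewhere | None |
| SAEs | All after the tracer | No separate route |

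The procedure covers only part of what is required.

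**2. Search for the period**

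- Table 1 (section 6.5.5.6) is broken in the text available, but its legible rows are FDA and IRB reporting times and forms. Its expedited limits run from discovery of the event: 7 days to the FDA and 10 days to the IRB. They say how fast to report, and do not say how long to look.
- Section 6.5.5.2 specifies no length for its follow-up period.
- Section 6.5.5.5 defers to the protocol or to outside guidance, and names no guidance that supplies a length.
- The manufacturer SAE duty in 6.5.5 has a start (receipt of tracer) and no end.

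Three references lead to a period that is not stated in any section.

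**3. Scale (illustration only)**

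Inputs from the documents:
- 15 patients (section 6.2) and two imaging exams each (section 3.5), so at most 15 × 2 = 30 injections.
- Tracer-associated events in at most 1% of patients (sections 6.5.5.3 and 6.5.5.4).

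Assumptions not in the documents:
- The 1% is applied per injection, and all of it is treated as occurring after departure.
- A share c of such events reaches the study team: 50% as the central value, with 25% and 75% as the range.
- Injections are independent.

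Formula: P(none recorded) = (1 − 0.01 × c)^30; expected number recorded = 30 × 0.01 × c.

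| c | P(none recorded) | Expected recorded |
|---|---|---|
| 100% | 0.99^30 = 74% | 0.30 |
| 75% | 0.9925^30 = 80% | 0.225 |
| 50% | 0.995^30 = 86% | 0.15 |
| 25% | 0.9975^30 = 93% | 0.075 |

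At the protocol's own rate, a record of no events is the likely outcome even with full capture. Halving capture moves its probability from 74% to 86%. The 1% describes tracer-associated events. The all-cause rate, which is what the definition in 6.5.5.1 covers, is not given, so the loss of all-cause events cannot be sized.

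**The case against.** The case on the other side is substantial, and most of it limits the point without removing it.

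- **Rates.** A reader might assume delayed events in 5–10% of injections. With half captured, the chance of recording none in 30 would then be 47% to 21%, against 21% to 4% with full capture. The documents do not support those rates for the tracer: they give at most 1%. If the higher rates are meant as all-cause, most of the events would come from cancer, its treatment or background illness and would say little about the tracer.
- **Timing of reactions.** Two of the three commonest reactions named in 6.5.5.3 are at the injection site. The checks in 4.6.4 and 6.5.5.1 are well placed to see these.
- **Other channels.** Events could surface through routine care at the same institution, at the second scan, or through the investigators' own duty in 6.5.5.2 to report suspected events. So the patient's call is the only route written for collecting events after departure, which is less than saying it is the only way an event could become known. None of the other channels is set up to ask about the interval.
- **Attribution.** A reader might infer that the patient takes over the causal judgement that 6.5.5.5 gives to the physicians. He does not: they still attribute every event that reaches them. His view affects only which events reach them.
- **Study results.** Safety is not among the endpoints in sections 5.1 to 5.3, and section 6.4 plans no analysis of event rates. No planned estimate is biased by this. The list in 6.5.5.3 also draws on the literature.

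What remains is the mismatch between an all-cause requirement and a cause-filtered route, and a period that is cited but not stated.

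**Conclusion.** The point holds as a minor one about safety ascertainment. After the patient leaves the imaging center, the written procedure cannot be relied on to deliver the all-cause events and all-cause SAEs that section 6.5.5 requires, and the period over which they are required appears nowhere in the documents. Events he does not link to the tracer may be missed.

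A reader might go further and conclude that delayed events will be under-counted by a material amount, or that the trial's findings are compromised. The documents do not support either conclusion. The direction of any loss follows from the text, but its size does not. With 1% per injection and half captured, the chance of an empty record in 30 injections is about 86% instead of 74%, a difference of 12 percentage points; with capture between 75% and 25% it is 80% to 93%. These figures rest on an assumed capture share and on reading a per-patient upper figure as a per-injection rate. The textual mismatch does not depend on them.

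**What to change.** 1. **Section 4.6.5.** Have the existing research coordinator ask each patient, whatever he thinks the cause, about any event or hospitalisation since the injection. Ask once on arrival for the second scan, and once by a brief contact after the second scan, dated to the end of the stated reporting period. Record the date of each event so that it can be placed inside or outside the period.
2. **Section 6.5.5.** The sponsor should state one reporting period counted from each injection. Use it in 6.5.5.1, 6.5.5.2 and 6.5.5.5 and for the manufacturer SAE reports, remove the pointer to Table 1, and reconcile 4.6.5 with it. The length is for the sponsor to choose and justify. The choice should take account of the second scan's timing, which is itself inconsistent (6–12 weeks after starting therapy in section 3.1, 3–6 months in section 4.6.2) and must also be reconciled.

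**Cost.** Protocol wording, one question at a visit already planned (at most 15) and one brief contact per patient (at most 15). No new staff or procedure is needed. The downside is that events due to cancer therapy or background illness will also be recorded, and the physician investigators will have to attribute them. The longer the period, the more of these there will be.
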